## **Materials:**

- 1- Platelet rich fibrin kit
- 2- Centrifuge device
- 3- 10 ml PRF tubes and A-PRF tubes
- 4- Two piece root form implant
- 5- Gelatin sponge

## **Surgical Procedures:**

After administration of Local anesthesia, gentle atraumatic extraction is performed for the nonrestorable tooth, followed by careful cleaning of the extraction socket. Drilling for the implant begins to create the correct depth and diameter for implant placement. The implant is installed according to manufactures instructions, ensuring proper seating and stability to promote integration with the surrounding bone.

**For Group A,** PRF preparation involves collecting 20 mL of venous blood into anticoagulant-free tubes, followed by centrifugation at 2,700-3,000 RPM for 8-12 minutes. This process separates the blood into layers, from which the fibrin clot is carefully extracted.

**For Group B,** A-PRF is prepared similarly but centrifuged at a lower speed (1300-1500 RPM) for 12-14 minutes to yield a higher concentration of platelets and leukocytes. After preparation.

PRF and A-PRF are applied to the implant site to aid tissue regeneration and integration. Application of Gelatin Sponge to cover the implant before suturing over the implant.

## **Key Differences Between PRF and A-PRF Preparation:**

- **Centrifugation Speed:** A-PRF is prepared at a lower speed compared to traditional PRF to yield a richer concentration of leukocytes.
- **Fibrin Clot Characteristics:** A-PRF tends to have a softer, more pliable fibrin network due to the different processing methods, which may enhance its handling during surgical application.
- **Cellularity:** A-PRF has a higher concentration of white blood cells, contributing to its potential benefits in promoting healing and reducing inflammation.

## **Post-operative phase:**

Apply gauze with light pressure to the surgical area to manage any bleeding. Instruct the patient to keep the gauze in place for 30–45 minutes and to replace it if bleeding persists.

## **Post-operative instructions:**

The patient will be advised to avoid chewing hard foods at the implant site for 2 months, maintain oral hygiene with soft tooth brush. And avoid touching or disturbing surgical site.

## **Post-operative medication:**

Includes Antibiotics (Augmentin: amoxicillin and clavulanic acid) 1g, Analgesics (Brufen; ibuprofen) is prescribed twice daily for 3 days, along with Anti-inflammatory tablets. Use of mouth wash (Orovex-H) rinse twice daily.

## **Prosthetic phase:**

Three months after implant placement, expose the fixture, followed by the placement of gingival formers for 1-2 weeks to shape the soft tissue around the implant collar, ensuring proper gingival contour. Impressions will be taken. Patients in both groups will receive final restoration, with the abutments secured to the implants, ensuring functional loading.

## **Evaluation:**

### **1) Clinical evaluation:**

#### **A) Implant Stability:**

Implant stability will be measured by Resonance Frequency Analysis (RFA) ISQ unit at 3 months and 6 months post-operative .

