### Sample size:

Using G power program version 3.1.9.7 to calculate sample size based on expected effect size of 2.02 (  $1.56 \pm 0.52$  &  $0.69 \pm 0.32$  ) depending ,using 2-tailed test ,  $\alpha$  error =0.05 and power = 95.0% , the total calculated sample size will be 16 divided into two groups.

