## **Study Design:**

For the study production the total number of the included patients will be 16 with respect to the inclusion criteria that is selected, patients will be randomly divided into two equal groups A&B, both of them will under-go Immediate implant placement each group will have its unique method of Filling up the jumping gap around the dental implant either by the use of Platelet-rich fibrin (PRF) or Advanced platelet-rich fibrin (A-PRF).

**Group A:** The jumping gap will be filled with Platelet-rich fibrin (PRF).

**Group B:** The jumping gap will be filled with Advanced platelet-rich fibrin (A-PRF).

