#### **B) Insertion torque:**

**Measurement Tools:** A torque wrench is used to measure the insertion torque during implant placement.

**Torque Values:** Generally, insertion torque values between 25-45 N/cm are considered optimal for primary stability. Lower torque values may indicate insufficient primary stability, while excessively high values (over 50 N/cm) could cause excessive stress on the surrounding bone.

**Comparative Analysis:** Compare the insertion torque values between the PRF and A-PRF groups to evaluate whether one preparation method offers superior initial stability, potentially affecting long-term outcomes.

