## **Statistical analysis:**

Data will be analyzed using SPSS (statistical package for social sciences) version 22. Qualitative data will be presented as number and percent, Quantitative data will be tested for normality by Kolmogrov-Smirnov test then described as mean and standard deviation for normally distributed data and median and range for non-normally distributed. The appropriate statistical test will be applied according to data type with the following suggested tests : Chi-Square for categorical variable , Student t test and Mann Whitney U test for continuous variables.

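### ISQ has no reading at placement, and insertion torque, the one baseline stability measure, is compared as if the filler could affect it instead of being used to adjust later ISQ

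*Protocol*

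**What the plan says.** Four parts of the protocol bear on this.

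- **Evaluation, Implant Stability:** "Implant stability will be measured by Resonance Frequency Analysis (RFA) ISQ unit at 3 months and 6 months post-operative". No other section adds a reading at placement.
- **Evaluation, Insertion torque:** "A torque wrench is used to measure the insertion torque during implant placement". The section links torque to primary stability ("insertion torque values between 25-45 N/cm are considered optimal for primary stability") and sets its purpose: "Compare the insertion torque values between the PRF and A-PRF groups to evaluate whether one preparation method offers superior initial stability". It adds that this may bear on long-term results.
- **Surgical Procedures:** the socket is cleaned and drilled and the implant is installed. Only after that does the text come to the filler: "PRF and A-PRF are applied to the implant site to aid tissue regeneration and integration".
- **Statistical analysis:** the tests suggested for quantitative data are "Student t test and Mann Whitney U test for continuous variables". No adjusted analysis is mentioned.

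Allocation is random and equal (Study Design: "patients will be randomly divided into two equal groups A&B"), with 16 patients in all. Both CBCT outcomes, unlike ISQ, have an immediate post-operative reading as well as one at 6 months.

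**The concern.** The filler can act only on what happens after the implant is seated. ISQ at 3 and 6 months reflects that effect together with how firmly the implant was held at the start. Without a placement ISQ the two cannot be separated on the ISQ scale, and the rise or fall since surgery cannot be described. Torque is in N/cm and cannot be subtracted from an ISQ value.

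The protocol does hold a measure of initial stability, and it regards initial stability as potentially prognostic. Yet it gives torque the role of an outcome. In the sequence described, a torque difference between arms cannot be an effect of PRF or A-PRF. Reporting it as evidence that one preparation gives better initial stability would misread a baseline imbalance as a treatment effect.

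At stake are a possible false statement about torque, and avoidable noise in the ISQ comparison of a 16-patient trial.

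**Working it through.** **1. The plan's own figure.** Sample size section: means 1.56 and 0.69, SDs 0.52 and 0.32, two-sided alpha 0.05, power 95%.

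- Pooled SD = √[(0.52² + 0.32²)/2] = 0.432.
- d = (1.56 − 0.69)/0.432 = 2.015, in line with the stated "expected effect size of 2.02".
- Two-sample t test (noncentral t) at d = 2.02: 7 per arm gives 93.4% power and 8 per arm gives 96.3%. The stated total of 16 is reproduced.

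The endpoint behind these figures is not named, so they supply no SD or effect size for ISQ. The figures below are therefore in SD units.

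**2. Chance imbalance at placement.** With 8 per arm, the standard error of the difference in mean primary stability is √(1/8 + 1/8) = 0.50 SD.

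- P(difference of at least 0.5 SD) = 2 × [1 − Φ(0.5/0.50)] = 2 × [1 − Φ(1)] = 31.7%.
- P(difference of at least 1 SD) = 2 × [1 − Φ(2)] = 4.6%.

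If the baseline correlates r with later ISQ within arms, an imbalance of 0.5 SD shifts the unadjusted ISQ difference by r × 0.5 SD: 0.15 SD at r = 0.3, 0.25 SD at r = 0.5 and 0.35 SD at r = 0.7.

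**3. Unadjusted power.** Assume a true ISQ difference of 1.2 SD. The noncentrality is 1.2 × √(8/2) = 2.4 with 14 df, which gives 60.8% power.

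**4. Power with a baseline covariate (ANCOVA, 13 df).** Two things change. The residual variance is multiplied by (1 − r²). Adjusting for a chance imbalance adds variance: for a normal covariate with 16 patients in two arms, the average factor is 1 + 1/12 = 1.083. Their product is the variance relative to the unadjusted comparison. Power comes from simulating the full ANCOVA (200,000 trials per row, normal data).

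| Assumed r | (1 − r²) × 1.083 | Simulated ANCOVA power | Unadjusted power |
|---|---|---|---|
| 0.2 | 0.96 × 1.083 = 1.04 | 58.9% | 60.8% |
| 0.3 | 0.91 × 1.083 = 0.99 | 61.2% | 60.8% |
| 0.5 | 0.75 × 1.083 = 0.81 | 69.6% | 60.8% |
| 0.6 | 0.64 × 1.083 = 0.69 | 76.1% | 60.8% |
| 0.7 | 0.51 × 1.083 = 0.55 | 84.7% | 60.8% |

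Leaving out the 1.083 factor would overstate the adjusted power by about 2 to 3 points.

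**5. Change from placement as the test.** With equal SDs at both times, the SD of the change is √[2(1 − r)]. This is 1.18 at r = 0.3 and 1.00 at r = 0.5. With 14 df, power for 1.2 SD is 47% and 61%. Testing change is therefore worse than the present plan at r = 0.3 and no better at r = 0.5.

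**The case against.** The case for leaving the plan alone has several parts.

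- **The unadjusted comparison is valid.** With random allocation, chance imbalance in primary stability is already in the standard error and the type I error rate. A reader might infer that the missing baseline biases the ISQ comparison. The documents do not support that. This stands: the loss is precision.
- **No stated aim fails.** The protocol promises no analysis of ISQ gain. A reader might also infer that no change in stability can be reported at all, but change from 3 to 6 months can be. Only change from placement is lost. This stands.
- **Primary stability is already recorded.** Torque would make an imbalance visible. That is true, but the protocol gives torque a different purpose, and torque cannot provide change in ISQ.
- **Adjustment belongs to the SAP.** The tests are only suggested, ISQ is not named among them, and a SAP not shown may adjust for torque. So it cannot be said that an unadjusted ISQ analysis is fixed. But a SAP cannot recover a reading that was never scheduled, and the stated purpose of torque is the protocol's own.
- **The gain is uncertain.** No correlation is given in the documents, and torque and placement ISQ may differ in how well they predict later ISQ. At r of about 0.2 adjustment costs a little power, and at r = 0.3 it gains almost nothing. If ISQ had the protocol's effect size of 2.02, unadjusted power would already be 96%. This stands and limits the size of the point.

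**Conclusion.** The point holds as a worthwhile improvement, not as an invalidating flaw. The schedule rules out ISQ gain from placement, and the purpose given to torque does not fit the described order of surgery. The suggested tests leave variation in primary stability in the ISQ comparison, with a 32% chance of an imbalance of 0.5 SD or more.

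At an assumed 1.2 SD effect, adjustment moves power from 61% to between 59% (r = 0.2) and 85% (r = 0.7). The gain is material only from r of about 0.5 upwards.

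The verdict assumes that the surgical steps are carried out in the order described. The power figures also assume normal data and a linear relation. One further condition applies: the lottery takes place right after extraction, so torque precedes the filler but follows allocation. Using it as a baseline assumes that knowledge of the arm does not change how the implant is seated.

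**What to change.** 1. In the Insertion torque section, describe torque as a baseline characteristic recorded before the filler is applied. Remove the statement that comparing it can show which preparation gives better initial stability.
2. Pre-specify ANCOVA of 3-month and 6-month ISQ, with arm as factor and insertion torque as covariate. This costs wording and one degree of freedom, with a slight loss of power if r is about 0.2 or less.
3. Preferably, add one ISQ reading after seating and before the filler is applied, and use it as the covariate instead of torque. This gives ISQ a baseline, as the CBCT outcomes already have. It costs one extra reading per patient, taken here to be short, with the type of device the plan already uses. It must be decided before enrolment, because it cannot be obtained later.
4. If that reading is added, report change from placement descriptively by arm, and do not use it as the between-group test.

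The sample size does not need to change for this point.

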#### **The index of ISQ 1-100**

-ISQ less than 60 = low stability.

-ISQ 60-70 = medium stability.

-ISQ more than 70 = high stability.

An ISQ value above 70 is generally considered a sign of good implant stability, while values below 60 may suggest caution before loading the implant.

#### **B) Insertion torque:**

**Measurement Tools:** A torque wrench is used to measure the insertion torque during implant placement.

**Torque Values:** Generally, insertion torque values between 25-45 N/cm are considered optimal for primary stability. Lower torque values may indicate insufficient primary stability, while excessively high values (over 50 N/cm) could cause excessive stress on the surrounding bone.

**Comparative Analysis:** Compare the insertion torque values between the PRF and A-PRF groups to evaluate whether one preparation method offers superior initial stability, potentially affecting long-term outcomes.

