## Materials and Methods

### Study setting:

This study will be conducted on (16) patients in the outpatient clinic of Oral and Maxillofacial Surgery department, Faculty of Oral and Dental Medicine, Delta University for Science and Technology. The selected patients has a badly decayed mandibular posterior teeth which needs to be extracted and require teeth replacement by dental implant. The selected patients will undergo immediate dental implant placement and platelet rich fibrin or advanced platelet rich fibrin will be used as a filling material in the jumping gap.

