## **Randomization:**

Each patient will be joined either to group A or B immediately after tooth extraction procedure through a random lottery mechanism (a startup number of 16 pre-printed paper for the first patient lottery, half of them with Platelet-rich fibrin (PRF) and the other with Advanced platelet-rich fibrin (A-PRF) with a probability of 50%) and the offending patient will choose the pre-printed paper with the specific procedure randomly and blindly.

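### Insertion torque is compared between arms as an effect of PRF or A-PRF, but on the described sequence it is read before the material is in place

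*Protocol*

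**What the plan says.** Under Evaluation, Clinical evaluation, B) Insertion torque, the Protocol fixes both the time of the reading and the use made of it. On timing: "A torque wrench is used to measure the insertion torque during implant placement". On use, the investigators are to "Compare the insertion torque values between the PRF and A-PRF groups to evaluate whether one preparation method offers superior initial stability", and the paragraph adds that this may bear on long-term outcomes.

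The role of the study material is set out elsewhere. Study setting says that "platelet rich fibrin or advanced platelet rich fibrin will be used as a filling material in the jumping gap". Study Design says that "each group will have its unique method of Filling up the jumping gap around the dental implant". The Introduction likewise places grafting material between the implant and the socket walls.

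Surgical Procedures describes extraction, socket cleaning and drilling, and then: "The implant is installed according to manufactures instructions, ensuring proper seating and stability to promote integration with the surrounding bone". The arm-specific clot preparation follows, and after it: "PRF and A-PRF are applied to the implant site to aid tissue regeneration and integration". Gelatin sponge and suturing come last.

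Two further statements matter. On allocation: "Each patient will be joined either to group A or B immediately after tooth extraction procedure through a random lottery mechanism". On the other stability measure: "Implant stability will be measured by Resonance Frequency Analysis (RFA) ISQ unit at 3 months and 6 months post-operative".

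**The concern.** The torque paragraph poses a causal question about the preparation, namely whether PRF or A-PRF gives better initial stability. An outcome can answer that only if it is measured once the preparation is able to act on it. Torque is read while the implant is being driven in. A filler that goes into the space around a seated implant is not yet there.

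A torque difference between the arms would then reflect chance or differences in how or where the implants were placed. Read as the protocol intends, it would support a claim of superior initial stability that the design cannot support. A null result has the mirror-image problem, since it says nothing about whether the two preparations are similar.

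**Working it through.** **Timing, from the text.**

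| Step | Source in the Protocol |
|---|---|
| Tooth extracted | Surgical Procedures |
| Arm drawn by lottery | Randomization |
| Site drilled, implant installed | Surgical Procedures |
| Torque read | Insertion torque (during placement) |
| Clot preparation described | Surgical Procedures |
| Material applied to the implant site | Surgical Procedures; Study setting and Study Design (gap around the implant) |
| Gelatin sponge, suturing | Surgical Procedures |
| First ISQ | Implant Stability (3 months) |

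No section puts PRF or A-PRF into the drilled site or onto the implant before insertion. On this sequence torque is read after allocation but before the allocated material is in place. The expected torque difference due to the material is therefore zero.

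**The plan's sample size, reproduced.** Sample size gives means and SDs of 1.56 ± 0.52 and 0.69 ± 0.32, a two-sided alpha of 0.05 and 95% power.

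- d = (1.56 − 0.69) / √[(0.52² + 0.32²)/2] = 2.015, against 2.02 stated.
- Exact two-sample t-test power at d = 2.015 is 93.2% with 7 per arm and 96.3% with 8 per arm.
- The total of 16 (8 per arm) is confirmed. It is not tied to torque.

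**What a torque test would do when the true effect is zero.** The assumption is a two-sided Student t test at 5% with 8 per arm. Statistical analysis suggests the t test or Mann-Whitney for continuous variables, and the torque paragraph names no test.

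1. Degrees of freedom: 8 + 8 − 2 = 14. Critical t = 2.145.
2. Smallest significant difference in pooled SD units: 2.145 × √(2/8) = 2.145 × 0.5 = 1.07.
3. Chance of a significant result: 5%, whatever the sample size.
4. Mean |t| given |t| > 2.145 is 2.66, so the mean standardised difference among chance-significant results is 2.66 × 0.5 = 1.33 SD.

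The document gives no SD for torque, so these figures cannot be turned into torque units.

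**The case against.** The strongest objection is that the surgical order is inferred. Surgical Procedures lists the steps common to both arms, then the two preparations, then application. That layout could be by topic and not by time. The Group B paragraph also ends in a broken fragment where a linking phrase might have stood, and applying material to the implant site does not by itself rule out earlier placement. This stands as a limit on certainty. It does not rescue the plan: the repeated description as filler of a gap around the implant favours the order used here, and on the other order the sections conflict.

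Second, the torque paragraph asks a question and sets no reporting rule, so a false conclusion is possible but not certain. That is fair. The question still cannot be answered by the comparison, and a statistical analysis plan that merely chose a test would not change this.

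Third, the 1.07 and 1.33 SD figures hold for any null t test with 8 per arm. That is true. They show how a chance finding would look and do not establish the flaw, which is the zero expected effect.

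Fourth, comparing torque between arms has some use as a check that primary stability was similar. That also stands, and a descriptive summary by arm serves it.

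Finally, because the arm is known before placement and no concealment from the surgeon is described, allocation could influence how the implant is placed. This is possible but not shown, its size cannot be derived from the document, and it would be bias and not an effect of the filler.

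**Conclusion.** The concern holds and should be fixed. On the sequence the Protocol describes, the filler's effect on insertion torque is zero and the planned inference about the preparation is wrong as written. If nothing else differs at placement, a 5% test would give a spurious difference in 5% of trials, typically of about 1.33 pooled SD with 8 per arm.

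This rests on reading Surgical Procedures in order and on the material being a filler around the seated implant. If the material is meant to be in place before insertion, the finding becomes a contradiction between Study Design, Surgical Procedures and Insertion torque.

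The reach is limited to one misdirected comparison. The ISQ, marginal bone loss and plate-thickness comparisons and the sample size are not affected.

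**What to change.** In the Insertion torque paragraph, remove the statement that the comparison shows which preparation gives better initial stability, and remove the between-group test. Report torque by arm as mean and SD, or median and range, as a descriptive measure of primary stability at placement. It is worth keeping because ISQ is first taken at 3 months, so torque is the only stability measure planned at that time. If the material is intended to be placed before insertion, reconcile Study Design, Surgical Procedures and Insertion torque so that the order is explicit. The cost is one reworded paragraph, or consistent wording across three sections, with no extra patients, visits or data.

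An optional step is to draw the lottery paper after the implant is seated and torque recorded, which would make torque a true pre-randomisation variable. Its cost is real: the arm-specific centrifugation (8–12 or 12–14 minutes in Surgical Procedures) could not start until then, which adds waiting during surgery. The core fix does not depend on it.

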#### **C) Biochemical assessment:**

Gingival cervical fluid marker a baseline and post-surgery.

## 2) Radiographic evaluation:

**A) Marginal Bone Loss:** A CBCT measurement will be done at immediate post-operative and after 6 months will also help assess the amount of marginal bone loss around the implant, which is a critical indicator of implant success. Measurements can be taken from the implant-abutment junction to the crest of the surrounding bone

**B) Buccal/Lingual plate of bone thickness:** A CBCT measurement will be done at immediate post-operative and after 6 months.

The measurement involves identifying the midpoint of the implant and drawing a perpendicular line from this point to the outer buccal cortical plate. This measurement helps evaluate the amount of buccal bone that remains after implant placement and is essential in predicting long-term implant stability and success, as thinner buccal bone can be more prone to resorption

